5.6.1 Replacement of patients

If a patient is withdrawn from the study for reasons other than drug-related toxicity or a positive skin prick test and has received less than three infusions of MOv18 IgE during Cycle 1, then this patient can be replaced. The withdrawn patient will be replaced by another patient who will be treated at the same dose level.

5.7 Concomitant medication and treatment

Concomitant medication may be given as medically indicated. Details (including doses, frequency, route and start and stop dates) of the concomitant medication given must be recorded in the patient's medical records and relevant details entered into the electronic case report form (eCRF). Prophylactic medication (antihistamine, antipyretic and/or corticosteroid), will be given ahead of the patient's **first and subsequent** infusions if considered medically appropriate by the PI and Sponsor (See Section 5.4).

Palliative radiotherapy may be given concomitantly for the control of bone pain or other symptoms. Irradiated lesions will not be evaluable for response.

The patient must not receive other anti-cancer therapy or investigational medicinal products during the study.

The following medications are not allowed and must be discontinued before starting study treatment and throughout therapy:

- Beta-blockers (which may counteract the therapeutic effects of adrenaline)
- Tricyclic anti-depressants or monoamine oxidase inhibitors (MAOIs) (which can dangerously augment the effects of adrenaline)
- Systemic immunosuppressive therapy (including any dose of systemic corticosteroids except when prescribed for prevention or treatment of infusion reactions to MOv18 IgE; inhaled corticosteroids are generally allowed)
- Bisphosphonates
- Herbal products, which may have an immunomodulatory effect (e.g. green tea), should generally be avoided but food supplements and homeopathic products are allowed
- Antihistamines (eg. hydroxyzine, cetirizine, loratadine, ketotifen), may interfere with skin prick testing and are not allowed before skin prick testing (see below for washout period). They may be used after a skin prick test when prescribed for prevention or treatment of infusion reactions to MOv18 IgE.
- Omalizumab, topical steroids or topical calcineurin inhibitors in the region used for skin prick testing. These may all interfere with skin prick testing

A washout period of at least four half-lives is required for beta-blockers, tricyclics and MAOIs before starting study medication. An appropriate washout period should be implemented for corticosteroids (e.g. a few days may be sufficient for low doses given for a short period for appetite stimulation). Patients who have been treated with bisphosphonates in the 18 months before starting study medication are excluded from the trial. Antihistamines should be stopped for at least four half-lives before each MOv18 IgE skin prick test. If required for prevention of infusion reactions, antihistamines must be given after the

skin prick test results are known. If needed to ensure adequate washout of an antihistamine, the MOv18 IgE dose may be delayed.

COVID-19 Vaccinations: Due to the lack of interaction studies with the COVID-19 vaccines and Immunotherapy IMPs, an appropriate wash our period of 1 week has been implemented following any COVID-19 vaccine and infusion with MOv18. This will be a 1-week washout following both the 1st and 2nd vaccine doses. Therefore, MOv18 infusions could take place in between the 2 vaccine doses if necessary, but MOv18 dosing would need to be delayed by 1 week after each vaccination. This washout period will be applicable to any COVID-19 vaccine approved for use by the MHRA.

6 PHARMACEUTICAL INFORMATION

6.1 Supply of MOV18 IGE

A complete certificate of analysis and a Qualified Person (QP) certification must be provided with each batch of MOv18 IgE (IMP) and be retained in the Pharmacy File.

For information on MOv18 IgE and re-ordering of supplies, contact the Clinical Research Associate (CRA)/Clinical Study Manager (CSM) responsible for the study who will arrange further supplies.

MOv18 IgE will be supplied by:

The primary and secondary packaging for the IMP will be labelled according to Eudralex Volume 4: Annex 13 'Investigational Medicinal Products' of the European Union guide to Good Manufacturing Practice (GMP). Prior to despatch of IMP to the clinical trial site a label detailing the investigator name and investigator site name will be added to the secondary packaging at the MIA (IMP) licensed manufacturer in accordance with GMP. An example of the labels can be found in the Pharmacy File.

6.2 Pharmaceutical data

6.2.1 Formulation of MOv18 IgE

MOv18 IgE will be supplied in glass vials as a sterile, pyrogen and particle-free clear colourless solution for dilution prior to infusion.

6.2.2 Storage conditions

All supplies must be stored in a secure, limited access storage area.

MOv18 IgE must be stored at 2-8°C and protected from light.

6.2.3 Method of reconstitution

6.2.3.1 Solution for intravenous (IV) infusion

Good aseptic practice must be employed when preparing MOv18 IgE solution for infusion.

The MOv18 IgE solution will be drawn from the supplied vial and injected into a bag for IV infusion containing 250 mL of saline. Please refer to the IMP Handling Guidelines for instructions on the preparation of solution for infusion.

6.2.3.2 Solution for skin prick testing

Solution for skin prick testing will be prepared for each patient from the supplied vial. The target concentration for skin prick testing is 2 µg/mL. Please refer to the IMP Handling Guidelines for instructions on the preparation of solution for skin prick testing.

As of Protocol Version 5.0, patients will only undergo skin prick testing prior to IV MOv18 IgE administration (prior to this, patients received a MOv18 IgE intradermal test dose).

6.2.4 Stability and labelling of the diluted MOv18 IgE

The prepared infusion bag must be stored at 2-8°C and used within 24 hours.

Labelling requirements for the diluted MOv18 IgE can be found in the IMP Handling Guidelines.

6.2.5 MOv18 IgE administration

Before administering MOv18 IgE, the exact dosage must always be double-checked by a second suitably qualified person. All checks and double-checks must be documented (signed and dated) and the documentation must be available for the CRA/CSM to verify.

6.2.6 Vein extravasation/accidental spillages

MOv18 IgE is not a vesicant. Extravasation and accidental spillages should be dealt with according to hospital policy.

6.3 MOv18 IgE accountability

Accurate records of all IMP (MOv18 IgE) shipments, vials dispensed, and all IMP returned must be maintained. This inventory record must be available for inspection at any time by CRAs or CSMs of the Centre for Drug Development (CDD). IMP supplies are to be used only in accordance with this protocol and under the supervision of the Investigator.

The Investigator undertakes not to destroy any unused IMP unless authorised to do so by the CDD. Any unused IMP must be destroyed according to hospital procedures (refer to the study IMP Handling Guidelines for exceptions to this) and properly accounted for using the IMP Destruction Form and also on the IMP Accountability Record. During the course of the study the CRA will check the numbers of vials of MOv18 IgE shipped to the centre, the number used and the number destroyed or returned. The pharmacy will give an account of any discrepancy.

The MOv18 IMP Handling Guidelines will describe any appropriate procedures relating to retention of IMP for investigations. If applicable, the retained IMP and vial should be fully accounted for, and any relabelling fully documented. Where the retained IMP is transferred to an analysing lab, this transfer should be documented appropriately.

7 INVESTIGATIONS SCHEDULE

In cases where a patient has investigations at a different hospital, for example weekly blood samples, then it is the Investigator's responsibility to ensure he/she receives and reviews the reported results. These results must be available for source data verification. Laboratory reference ranges, including effective dates, and evidence of laboratory accreditation must be obtained from all laboratories used.

7.1 Pre-treatment evaluations

Details of all evaluations/investigations for enrolled patients, including relevant dates, required by the protocol must be recorded in the medical records so that the eCRF can be checked against the source data.

Please also refer to the tabulated Schedule of Assessments in Section 7.6.

7.1.1 Archival tumour testing for FR α

An archival tumour specimen must be sent to the central analysing laboratory for assessment of FR α expression by immunohistochemistry (IHC) prior to enrolment on the study. Otherwise, there is no time limit for this assessment. A separate 'FR α testing on stored tumour sample informed consent' is required. 1+, 2+ or 3+ membrane staining on at least 5% of tumour cells is required for inclusion of the patient in the study. For patients with no archival specimen available, a pre-treatment tumour biopsy is mandatory. Such patients will need to consent using section B of the 'Alpha Folate Receptor' informed consent' form.

7.1.2 Obtaining written informed consent

Written informed consent must be obtained from the patient using the 'Main study consent' form before any protocol-specific procedures are carried out, other than archival tumour testing for FR α expression which may be performed prior to obtaining written informed consent for the main study (see Section 7.1.1). The patient must be given adequate time to think about their commitment to the study. If more than 28 days has passed since informed consent was obtained before the start of MOv18 IgE dosing then the Investigator should consider whether repeat consent should be obtained from a patient.

Only the Principal Investigator (PI) and those Sub-Investigator(s) delegated responsibility by the PI, and have signed the Delegation Log, are permitted to gain informed consent from patients and sign the consent form. All signatures must be obtained before the occurrence of any medical intervention required by the protocol (ICH GCP 4.8.8 and 8.3.1.2). The patient should sign in the presence of the PI/Sub-Investigator, therefore the date of the signatures of both the patient and the PI/Sub-Investigator should be the same.

The PI or the Sub-Investigator must inform the patient about the background to, and ensure that the patient is aware of, the following points:

- The known toxicity of the IMP and the possibility of experiencing side-effects.
- That IMP is new and that the exact degree of activity is at present unknown, but that treating him/her will contribute to further knowledge.
- The potential dangers of becoming pregnant (or the patient's partner becoming pregnant) and he/she has been given information about appropriate medically approved contraception (refer to Section 9.7).
- That he/she may refuse treatment either before or at any time during the study and that refusal to participate will involve no penalty or loss of benefits to which they are otherwise entitled.

- The options for routine management of their cancer.
- Whom to contact for answers to pertinent questions about the research and their rights, and also who to contact in the event of a research-related injury.

A copy of the consent form and patient information sheet must be given to the patient to keep and the original consent form and patient information sheet, must be filed in the Investigator Study File (ITF) (unless otherwise agreed that the original consent form will be filed in the medical records and the copies kept in the ITF).

7.1.3 Evaluations within 28 days (Day -28 to Pre-dose on Day 1)

The following must be performed/obtained **within the 28 days before** the patient receives the first infusion of MOv18 IgE. Existing results may be used even where these investigations were performed prior to the patient's provision of informed consent for the study if they were performed within the required time window.

- **Demographic details**
- **Medical history** including prior diagnosis, prior treatment, concomitant diseases and baseline signs and symptoms, concomitant treatment
- **Radiological disease assessment** per RECIST 1.1 (see Appendix 3) including a computerised tomography (CT) scan or magnetic resonance imaging (MRI) scan of the chest, abdomen and pelvis, with additional investigations as clinically indicated
- **Tumour marker**, if applicable for tumour type
- **Full physical examination**, including clinical examination and measurement of palpable or visible tumour lesions per RECIST 1.1 (see Appendix 3)
- **WHO performance status**
- **Height and weight**
- **Vital signs** (blood pressure (BP), pulse rate and temperature)
- **Electrocardiogram (ECG)**
- **Urine sample for urinalysis** - glucose, protein and blood
- [REDACTED]

Note that all adverse events (AEs), including serious adverse events (SAEs), must be monitored and recorded in the eCRF from the time the patient consents to any protocol-specific procedure (see Section 9 for further details).

7.1.4 Evaluations within seven days (Day -7 to Pre-dose on Day 1)

The following must be performed **within seven days before** the patient receives the first dose and results must be confirmed prior to the patient receiving IMP:

- **Blood sample for clinical laboratory tests:**
 - Haematology – haemoglobin (Hb), white blood cells (WBC) with differential count (neutrophils and lymphocytes) and platelets

- **Coagulation screen** (international normalised ratio (INR), and activated partial thromboplastin time (APTT) value or ratio)
- Biochemistry – sodium, potassium, corrected calcium, phosphate, urea, creatinine, total protein, albumin, bilirubin, alkaline phosphatase (alk phos), alanine aminotransferase (ALT) and aspartate aminotransferase (AST), uric acid
- Female patients able to have children must have a negative result on a human chorionic gonadotropin (HCG) **pregnancy test** (serum or urine test is acceptable)
- **Blood sample for serum tryptase** and basophil activation test (BAT)
- **Research blood samples** – as described in Table 6 Summary of PK and PD Assessments.

7.2 Evaluations during the study

Please refer to Table 6 Summary of PK and PD Assessments and Table 7 Volume of blood required for study-specific tests (see Section 8.3) and to the Study Laboratory Manual for the details of the timing and handling instructions for research blood and tumour biopsy samples.

7.2.1 Safety evaluations with EVERY administration of MOv18 IgE

- **Adverse events and concomitant treatments:**

Before each MOv18 IgE administration, an assessment of any AE experienced or changes in concomitant treatment since the previous visit must be made by the Investigator or Research Nurse. The start and stop dates of an AE together with the Investigator's assessment of the relationship of the event to treatment with MOv18 IgE and details of concomitant treatments must be recorded in the medical records. All AEs must be graded according to NCI-CTCAE Version 4.02.

- **Skin prick testing with MOv18 IgE**

As of Protocol Version 5.0, skin prick testing has been selected for optimal detection of potential anaphylaxis to MOv18 IgE. Site staff performing the skin prick test doses will first be trained in this technique by an Allergy nurse experienced in skin prick testing for sensitivity to allergens (once staff are trained, with the site Principal Investigator's approval, they may train other colleagues in the technique).

For this test, one drop of a 2 µg/mL solution of MOv18 IgE will be placed on onto the forearm skin. Please refer to the IMP Handling Guidelines for instructions on the preparation of the solution for administration. Alongside this test dose, a positive histamine control and a negative saline control will be required. Please refer to Skin Prick Testing Method in Appendix 8 for detailed guidance on the method of administration and interpretation of results. Response to the skin prick test should be checked at 15, 30 and 60 minutes post initiation of the skin prick test, prior to the start of every infusion of MOv18 IgE. If the skin prick test is positive at ANY of the three time points, that will constitute a positive result. Absence of a weal and flare reaction will allow the IV dose to be administered with the expectation that the risk of anaphylaxis is very low.

- In case of a positive reaction, no further MOv18 IgE will be given and the patient will be followed up for safety and then withdrawn from the trial (see Section 11; and Section 5.5.4 for possible exceptions to this rule). In case of a positive skin test, the following additional samples should be taken:

- Serum tryptase (immediately*, 2 and 6 hours post onset),
- BAT assay (immediately* post onset),

- PK (immediately*, 2 and 6 hours post onset),
- [REDACTED]

*or as soon as possible after onset.

Additional exploratory tests may be performed on these existing samples to elucidate the cause of the reaction on the day of the reaction. Further blood draws may be collected at other time points, as deemed appropriate by the TSG, with the patients documented consent in the patient notes. Approximately 45 mL of additional blood may be collected.

In case of uncertainty as to whether a skin prick test is positive or negative, advice will be sought from the Clinical Immunology team.

- **Vital signs** (BP, pulse rate and temperature) should be performed as clinically indicated and
 - Within the 30 minutes pre-dose
 - Every 15 minutes during the infusion for the first two infusions at least (see Section 5.3.1) and for those patients enrolled in the intra-patient dose escalation part of the trial, monitoring will be performed on Cycle 2 (doses 1 and 2) as per Cycle 1.
 - 15 minutes and 30 minutes after completion of the infusion
 - Before discharge from the clinic.
- **Monitoring with a pulse oximeter** continuously throughout the infusion until 30 minutes after completion of the infusion.
- **ECG** after completion of the infusion.
- **Blood sample for serum tryptase** test – taken on completion of the infusion.

Patients should remain in the clinic for observation for at least one hour after every dose of MOv18 IgE (6 hours for a positive skin prick test).

7.2.2 Additional evaluations for the first administration of MOv18 IgE on Cycle 1 Day 1

- **Vital signs** (BP, pulse rate and temperature) should be performed as described in Section 7.2.1 and additionally
 - 1h, 2h, 4h, 8h, 12h (± 1 hour), 18h (± 2 hour) and 24h (± 2 hours) after completion of the infusion
- **Blood sampling for PK** assessment of circulating MOv18 IgE in serum: 3.5 mL blood sample at 6 time points: Pre-dose, and 30 min (± 5 min), 2 h (± 30 min), 4 h (± 30 min), 6 h (± 30 min), 24 h (± 2 h). It is possible that the 30 min sample may be substituted for a 48 h (± 2 h) time point in later cohorts – see study lab manual) post-dose. If a time point has been missed, a sample should be taken as soon as possible and the time recorded.

For patients enrolled in the intra-patient dose escalation, these additional evaluations will also be performed on Cycle 2 Day 1.

7.2.3 Weekly and fortnightly clinic visits

Patients will be reviewed **weekly (± 2 days)** prior to each dose of MOv18 IgE (fortnightly ± 2 days during maintenance MOv18 IgE, if given) and the following tests and procedures will be performed:

- **Symptom-directed physical examination**

- **Assessment of adverse events and concomitant medication**
- **WHO performance status**
- **Blood sample for clinical laboratory tests:** Haematology and biochemistry must be performed within 24 hours (± 4 h) before each dose of MOv18 IgE and until 4 weeks after the last dose. At a minimum:
 - Haematology – haemoglobin (Hb), white blood cells (WBC) with differential count (neutrophils and lymphocytes) and platelets
 - Biochemistry - sodium, potassium, calcium, phosphate, urea, creatinine, total protein, albumin, bilirubin, alk phos, ALT or AST, uric acid.
- **Research blood samples** – as described in Table 6 Summary of PK and PD Assessments.
- [REDACTED]
- [REDACTED]
- [REDACTED]

7.2.4 Prior to the start of a new cycle of MOv18 IgE treatment (within 24 h before start of infusion on Day 1)

- **Urinalysis** –glucose, protein and blood
- **Tumour marker**, if appropriate for tumour type
- **Assessment of disease response:** required every 2 cycles (6-weekly) based on clinical examination, tumour marker, and CT/MRI for patients with measurable disease. Response will be assessed by RECIST 1.1 criteria (see Appendix 3), as well as by CA125 or other tumour marker (Rustin, 2003) if applicable.

For patients receiving maintenance MOv18 IgE, these tests/assessments should be repeated after 6 weeks (i.e. after the third maintenance dose, if given).

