3 STUDY DESIGN

3.1 Study objectives and endpoints

Primary Objectives	Endpoints
To assess the safety and tolerability of MOv18 IgE	
 • AEs and DLTs • Dose-independent significant toxicity (Section 3.3.2) • SAEs • Laboratory parameters 
AEs, SAEs and laboratory abnormalities will be graded according to NCI-CTCAE Version 4.02.
 
Causality of AEs/SAEs will be assessed by the investigator. Infusion-related events will be categorised as due to IgE-mediated mast cell degranulation (anaphylaxis) or cytokine release syndrome.

Secondary Objectives	Endpoints
To determine a recommended dose for Phase II evaluation	The recommended phase II dose (RP2D) will be based on safety data (the Maximum Tolerated Dose [MTD]; see definition in Section 3.4), and/or efficacy data (the dose at which evidence of anti-tumour activity is seen), and/or pharmacodynamic data, or will be the maximum evaluated dose (50 mg).
To document possible anti-tumour activity in patients treated at doses likely to be pharmacologically active	
Best response (according to RECIST 1.1) in patients receiving at least one dose of MOv18 IgE
 
CA125 response in patients with elevated CA125 at baseline

To describe the pharmacokinetics of MOv18 IgE	Serum concentrations of MOv18 IgE
Tertiary Objectives	Endpoints
[REDACTED]	[REDACTED]

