4.1.1 Inclusion criteria

1. Histologically or cytologically-proven advanced, unresectable solid tumour of a type known to express FR α in a percentage of cases (see [Section 2.4.2](#)).
2. Archival tumour tissue expressing FR α (1+, 2+ or 3+ membrane staining on at least 5% of tumour cells by immunohistochemistry using the BN3.2 antibody, based on the technique described by Lawson & Scorer, 2010).
3. Advanced disease for which no alternative therapy is felt to be appropriate.
4. Measurable disease or disease evaluable by tumour marker. Measurable disease is preferred for patients entering higher cohorts to facilitate efficacy assessments.
5. World Health Organisation (WHO) performance status of 0 or 1 (Appendix 1) and a life expectancy of at least 12 weeks.
6. Haematological and biochemical indices within the ranges shown below. These measurements should be performed within 7 days before the first dose of MOv18 IgE (Day -7 to Pre-dose on Day 1). Measurements performed before Day -7 may be accepted by the CDD to demonstrate eligibility if repeat testing is logistically difficult for the patient and is not considered necessary medically in the opinion of the Investigator or CDD.

Laboratory Test	Value required
Haemoglobin (Hb)	≥ 9.0 g/dL
Absolute neutrophil count	$\geq 1.5 \times 10^9$ /L
Platelet count	$\geq 100 \times 10^9$ /L
Serum bilirubin	$\leq 1.5 \times$ upper limit of normal (ULN)
Alanine aminotransferase (ALT) and aspartate aminotransferase (AST)	$\leq 2.5 \times$ ULN unless raised due to liver metastases in which case up to 5 x ULN is permissible
Serum creatinine	$\leq 1.5 \times$ ULN

7. Aged 16 years or over at the time consent is given.
8. Written (signed and dated) informed consent and capable of co-operating with treatment and follow-up.

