7.3 Evaluations at First Post-treatment Safety Assessment (28 ±7 days after final dose)

Evaluations at the First Post-treatment Safety Assessment must be performed 28 ±7 days after the final infusion of MOv18 IgE. The following investigations should be done:

- **Symptom-directed physical examination**
- **WHO performance status**
- **Weight**
- **Vital signs**, if clinically indicated
- **ECG**

- **Blood sample for clinical laboratory tests** – Haematology and Biochemistry parameters as detailed in Section 7.1.4
- **Urine sample for urinalysis** – glucose, protein and blood
- **Assessment of AEs and concomitant treatments**
- **Assessment of disease response**: if not performed within previous 28 days per RECIST based on clinical examination, tumour marker, and CT/MRI for patients with measurable disease. Response will be assessed by RECIST 1.1 criteria (see Appendix 3), as well as by CA125 or other tumour marker (Rustin, 2003) if applicable.
- **Tumour marker**, if appropriate for tumour type
- **Research blood samples** as described in Table 6 Summary of PK and PD Assessments (see Section 8.3).

Patients who receive MOv18 IgE as a skin prick test only should be followed for safety until resolution or stabilisation of any AEs/SAEs associated with MOv18 IgE.

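### The pre-dose chemistry minimum accepts ALT or AST without fixing which, while eligibility, baseline and the 28-day visit use both, so an isolated rise in the other enzyme could be missed during dosing

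*Protocol*

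**What the plan says.** Section 7.2.3 requires chemistry "before each dose of MOv18 IgE and until 4 weeks after the last dose. At a minimum", and then lists: "Biochemistry - sodium, potassium, calcium, phosphate, urea, creatinine, total protein, albumin, bilirubin, alk phos, ALT or AST, uric acid". It names no preferred transaminase and does not ask for consistency within a patient or a site.

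The other places ask for both enzymes:
- Section 4.1.1, inclusion criterion 6, applies its upper limit to ALT and to AST (2.5 x ULN, or up to 5 x ULN with liver metastases).
- Section 7.1.4, the baseline panel, lists "alanine aminotransferase (ALT) and aspartate aminotransferase (AST), uric acid", with calcium given as "sodium, potassium, corrected calcium, phosphate".
- Section 7.3, the visit 28 ±7 days after the final dose, asks for "Haematology and Biochemistry parameters as detailed in Section 7.1.4", and so takes over the baseline panel.

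Table 4 footnote (c) and Table 5 footnote (b) repeat the pre-dose timing but list no analytes. Section 3.1 makes laboratory parameters an endpoint of the primary objective and states that "AEs, SAEs and laboratory abnormalities will be graded according to NCI-CTCAE Version 4.02".

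**The concern.** A primary safety endpoint should be measured during exposure in the same way as before and after it. Here the least demanding transaminase requirement applies while patients are being dosed and while decisions are taken on the results. Three rules depend on a graded value or on a comparison with baseline:

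- **DLT count (Section 3.3.1).** Related non-haematological Grade 3 or 4 toxicity in the first three weeks can count.
- **Intra-patient escalation (Section 5.4.1).** A related adverse event of Grade 2 or higher in Cycle 1 generally holds the patient at the same dose. Section 9.2.1 allows a laboratory observation to be an adverse event, and Table 3 plans one patient per cohort.
- **Dose delay (Section 5.5.2).** The next infusion waits until toxicity is back to Grade 1 or less, or to baseline.

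If a site measures only AST, an isolated ALT rise is not graded at that visit. If ALT was raised at one visit and only AST is reported at the next, recovery of ALT cannot be shown. Patients with liver metastases may enter with raised transaminases, so for them the comparison with baseline matters most.

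An analysis plan cannot repair this, because an enzyme that was not assayed cannot be recovered.

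**Working it through.** No sample size, power or error rate bears on this point. The check compares the panels and then counts the visits under each.

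**1. Panels side by side**

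| Item | Baseline (7.1.4) and 28-day visit (7.3) | Pre-dose minimum (7.2.3) |
|---|---|---|
| Sodium, potassium, phosphate, urea, creatinine, total protein, albumin, bilirubin, alkaline phosphatase, uric acid | required | required |
| Transaminases | ALT and AST | either one |
| Calcium | corrected | not labelled corrected |

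Two items differ. Albumin is in both panels, so corrected calcium can be derived at every visit and no information is lost. The missing transaminase cannot be derived from anything else in the panel. The eligibility table in Section 4.1.1 has limits for ALT and AST but no calcium criterion, so calcium plays no part there.

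**2. Visits governed by the minimum**

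The clinical laboratory column of Table 7 has 15 mL at baseline and 10 mL at each of seven later time points (doses 1 to 6 and the 28-day visit): 15 + 7 × 10 = 85 mL, which is the total the table gives. That makes 8 time points. The fuller panel applies at baseline and at the 28-day visit, so the minimum governs 8 − 2 = 6. With three maintenance doses the figures are 6 + 3 = 9 of 8 + 3 = 11.

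**3. Where these visits fall**

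On the weekly schedule dose n falls on day 1 + 7(n − 1). Doses 2, 3 and 4 fall on Days 8, 15 and 22, and dose 6 on Day 36.
- The scheduled post-exposure chemistry for the three-week DLT window is the sample before dose 2 and the one before dose 3, with the sample before dose 4 at its close. All three are under the minimum.
- The same samples are the scheduled chemistry for the Cycle 1 review before intra-patient escalation. The samples before doses 5 and 6, taken during Cycle 2, are also under the minimum.
- For a patient who completes six weekly doses, both enzymes are next required at Day 36 + 28 ± 7, that is Days 64 ± 7, or Day 57 to Day 71. This is well after the cohort decision, which Section 5.4 bases on the three weeks from first dosing.

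**4. What cannot be computed**

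The documents give neither the share of transaminase rises confined to one enzyme nor the share of sites that would measure only one. No missed fraction can be derived.

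**The case against.** The strongest reply is that Section 7.2.3 sets a floor. Sites may run both enzymes, and many may do so. A fuller panel at screening, where both enzymes carry an eligibility limit, with a leaner one for monitoring is a coherent choice. Section 7 also foresees weekly bloods at other hospitals, where flexibility may be practical, although the protocol does not give that as a reason. This stands as far as it goes. But the floor is all the protocol guarantees, a site that measures one enzyme complies, and even a lean panel could fix which one.

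A reader might infer that hepatic toxicity would go undetected. The documents do not support that. One transaminase, bilirubin and alkaline phosphatase are required before each dose, adverse events are reviewed before each dose (Section 7.2.1), and both enzymes return at the 28-day visit. The gap is an isolated rise in the unmeasured enzyme during dosing.

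A reader might also infer that one missed value turns one DLT in three into none in three. That skips the filters in Section 3.3.1: the event must be probably or highly probably related, and transient, asymptomatic Grade 3 biochemistry judged not clinically significant is excluded. Many isolated rises would fall out there. Section 5.4.1 does not state that exclusion for its Grade 2 gate. There the Trial Steering Group keeps case-by-case discretion, but it can weigh only what was measured.

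A third tempting reading is that on-treatment calcium would be compared with a baseline on another scale. Nothing in the protocol says it will be analysed uncorrected, and the albumin needed for the correction is in the same panel.

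**Conclusion.** The transaminase requirement in Section 7.2.3 is inconsistent with Sections 4.1.1, 7.1.4 and 7.3, and no other part of the protocol resolves the difference. It affects 6 of 8 laboratory time points in the Initial Dosing Period (9 of 11 with maintenance), including all scheduled post-exposure chemistry in the DLT window. The consequence is limited: at sites that follow only the minimum, an isolated rise in the unmeasured enzyme may be missed, or return to baseline may not be demonstrable. This rests on some sites measuring a single enzyme, which the protocol permits but does not require. The frequency is unknown. Severity is minor, and the change is worth making because it is cheap. The calcium difference is one of wording only.

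**What to change.** In Section 7.2.3, replace the biochemistry list with a reference to the biochemistry panel in Section 7.1.4, as Section 7.3 already does. ALT and AST are then both measured before each dose, and the calcium label is aligned by the same edit. No dose, escalation or withdrawal rule changes.

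The cost is one more analyte on a sample already drawn, with no additional visit. Where pre-dose bloods are taken at an outside hospital, the second enzyme may need a specific request.
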